Remote consent may be obtained from a participant or guardian who has the proper guardianship documents in place. Assent may also be obtained in person or from the study participant via Zoom. If the participant declines assent, no additional study procedures will occur. The study team recognizes that remote consent / video conferencing will not be appropriate for all participants. Participant's preference for consent administration will take priority, unless the independent witness determines that a preference for remote consent / assessment is not appropriate for a given individual.

A participant's status will be considered 'Enrolled' once results from screening are available and reviewed, and the participant attends the Baseline visit.

Study Visits and Activities.

The initial screening visit will include assessments to ensure each participant is in overall fair health and would not have any additional or unnecessary risks while taking Tofacitinib. These screening assessments include: skin assessment to officially diagnose any immune skin condition, complete physical exam, collection of vitals, chest radiographs, ECG, pregnancy test for females if not surgically sterile or two years

post-menopause, and tuberculosis test. A blood draw will be performed for basic safety monitoring labs, which include hematology (CBC with WBC differential) and standard blood chemistry to assess hemoglobin, serum creatinine, bicarbonate, creatine phosphokinase, liver function (ALT, AST, ALP, albumin, bilirubin), and lipids (LDL, HDL, triglycerides, cholesterol). Blood draws are non-fasting. If a clinically relevant LDL, HDL, or triglycerides measure is obtained *after* the Baseline visit, a fasting draw will be obtained for follow-up. At the screening visit, viral surveillance for CMV, HSV1&2, and EBV will also be performed, as well as screening for HIV and hepatitis. TSH will also be drawn at screening, 8-weeks, and 16-weeks, as well as at 28 and 40 weeks for those in the Extension Arm, for those with positive thyroid autoantibodies at screening or a known hypothyroid diagnosis, to give clinical relevance to the AITD autoantibodies. See Table 1 for minimum score for inclusion criteria for each skin condition and Table 2 for list of safety labs collected. Study doctors may offer a skin numbing cream before all study related blood draws.

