Informed consent and assent forms will also be obtained before or at the screening visit. After receiving results from all screening tests and confirming eligibility, a study doctor will prescribe Tofacitinib from the UCHealth or CU Anschutz Medical Center Investigational Pharmacy. We anticipate participants will return for their baseline visit within approximately four weeks of their screening visit. If the duration between Screening and Baseline visit is longer than 4 weeks, study doctors may order screening labs again at their discretion. At the baseline visit, participants will be instructed to begin administration of oral Tofacitinib at 5 mg BID the following morning. Study visits are timed at Time 0 (baseline), 2, 4, 8, 12, and 16-weeks throughout the course of treatment, as well as 2 weeks after ending treatment (18 weeks in total to complete study visits). Participants in the Extension Arm will have an additional visit at 28 weeks with the final follow-up visit at 40-week. Each study visit will occur +/- 3-days of this schedule determined from Time 0 (baseline), except for Extension Arm visits that will occur +/- 7 days of the ideal visit schedule. Missed study visits or visits that occur outside of this window will be reported as a protocol deviation/violation and will not change the original schedule. A missed study visit that was supposed to include dispense of Tofacitinib should be rescheduled, even if outside the allowed window. Study doctors will not continue the Tofacitinib prescription without current safety labs.

Condition	Assessment	Minimum score
Moderate-to-severe atopic dermatitis	Eczema Area and Severity Index (EASI)	≥ 16
Alopecia areata affecting at least 25% of the scalp	Severity of the Alopecia Tool (SALT)	≥ 25
Moderate-to-severe hidradenitis suppurativa	Hidradenitis suppurativa - Physician's Global Assessment (HS-PGA)	≥ 3
Moderate-to-severe Psoriasis	Psoriasis Area and Severity Index (PASI)	≥ 10
Moderate-to-severe Vitiligo	Vitiligo Extent Tensity Index (VETI)	≥ 2

Table 1. Minimum score for inclusion criteria for each skin condition.

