Each visit will entail a physical exam, collection of vital signs, recording and monitoring of adverse events (AEs, see below), and a blood draw for the same battery of safety monitoring labs described in the screening procedures above. A follow-up ECG will be performed for all participants at the 4-week visit and as needed based upon concomitant medications at the study doctor's discretion. An audiogram will be performed before beginning treatment and after 15-16 weeks of treatment, to ensure Tofacitinib has not impacted hearing. A recent audiogram performed within the past 12 months for clinical reasons can be provided or accessed by the study team will be accepted, given that the appropriate elements were evaluated and no change in hearing status is anticipated. A negative Quantiferon Gold, Quantiferon Gold Plus or Quantiferon Gold HA and chest x-ray that have been obtained for clinical reasons within the past 12 months will be accepted for screening purposes if no change in TB status is anticipated. Participants will receive a tuberculosis screen at least every 12 months while in the study. Outside laboratory results will be accepted at the study doctor's discretion (Figure 6). Every effort will be made to have the same study doctor meet with a participant at each visit to minimize interrater bias. Skin conditions will be formally assessed at screening, baseline, 8, and 16 weeks by a dermatologist using standard and accepted metrics, such as: Investigator's Global Assessment (IGA) and Dermatology Life Quality Index (DLQI) for all skin conditions, Eczema Area and Severity Index (EASI) for AD, Severity of Alopecia Tool (SALT) for AA, Modified Sartorius Score (MSS) for HS, Psoriasis Area and Severity Index (PASI) for psoriasis, and Vitiligo Extent Tensity Index (VETI) for vitiligo. Note that the Hidradenitis Suppurativa – Physician's Global Assessment (HS-PGA) will be used to determine eligibility for participants with HS at screening and for EA qualification, while the MSS will be ongoing. Photographs will also be taken of the affected area(s) at the time of these assessments for additional validation of skin condition and visual, qualitative indicators of improvement or progression. Photographs may be taken at other safety visits to document response to treatment at the study doctor's discretion. Open-source online scoring calculators may be used to calculate skin condition severity, provided no PHI is entered. Participants in the Extension Arm will also have a formal skin assessment at 28 and 40 weeks.

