On very rare occasions, research labs are unable to be collected, or are only partially collected, due to participant dehydration or poor venous blood access. For participants co-enrolled in the Human Trisome Project (15-2170), research samples may be collected using a non-invasive capillary blood Tasso device as approved in that protocol, with samples transferred to this study for research purposes. If participants choose not to enroll in the Human Trisome Project, research samples will not be collected. Follow-up blood collection for research purposes must include the same collection method as obtained at Baseline visit, if possible.

Study data is collected and recorded in both electronic and paper format. Study visit data are recorded in REDCap, a HIPAA compliant online system administered locally by CU Anschutz. Study visits utilizing the CTRC are requested through the CU-Anschutz Oncore study management system, which contains study visit schedule, visit procedures, and integrates with the electronic medical record (Epic) and financial billing. Study visit procedure details are also documented in Epic.

Combined Screening and Baseline Activities.

If all screening labs and procedures are completed so that the participant is deemed eligible and can begin tofacitinib within five days of the blood draw, the laboratory values from the Screening Visit blood draw will be used for Baseline values. In this instance, an additional Baseline blood draw or formal skin assessment will not be required, except at the study doctor's discretion.

Safety Labs Collected	Version Date Implemented	Screening Visit 1	Baseline Visit 2	2-week Visit 3	4-week Visit 4	8-week Visit 5	12-week Visit 6	16-week Visit 7	2-week post Visit 8%	28-week Visit E28	40-week Visit E40
Chest X-ray	02.20.2020	X	N/A	N/A	N/A	N/A	N/A	N/A	N/A	N/A	N/A
ECG	02.20.2020	X	N/A	N/A	X	N/A	N/A	N/A	N/A	N/A	N/A
Audiogram	02.20.2020	X	N/A	N/A	N/A	N/A	N/A	X	N/A	N/A	N/A
Pregnancy Test [^]	04.22.2021	X	X	N/A	X	X	X	E	N/A	E	N/A
Complete Blood Count (CBC)	02.20.2020	X	X	X	X	X	X	X	X	E	E
Comprehensive Metabolic Panel	02.20.2020	X	X	X	X	X	X	X	X	E	E
Lipid Panel	02.20.2020	X	X	X	X	X	X	X	X	E	E
Creatinine Phosphokinase	02.20.2020	X	X	X	X	X	X	X	X	E	E
Quantiferon TB Gold Plus	02.20.2020	X	N/A	N/A	N/A	N/A	N/A	N/A	N/A	N/A	N/A
Virology (EBV IgG/IgM, CMV IgG/IgM, VZV IgG, HIV 1 and 2, HCV, HSV Type 1 &2 IgG, Hep B Surface Antigen/Core Antibody)	02.20.2020	X	N/A	N/A	N/A	N/A	N/A	N/A	N/A	N/A	N/A

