Thyroid Stimulating Hormone (TSH)	11.12.2020	X	N/A	N/A	N/A	*	N/A	X	N/A	X	X

Table 2. Schedule of safety labs. 'X'= Test performed; N/A = Not applicable. % This visit only occurs for participants who ended Tofacitinib treatment at Visit 7. E = Extension arm only visits * Follow-up required only if Screening Visit results are positive or participant is known thyroid dysfunction . ^ For females if not surgically sterile or two years post-menopause.

Visit 7 Considerations for the 16-week Endpoint.

If a participant misses 15% or more of Tofacitinib doses (3 or more pills) in the 7 days before a scheduled Visit 7 for any reason, Visit 7 will be rescheduled to ensure 7 days of compliant study drug intake before this endpoint visit. This may be outside the original +/- 3 days window for Visit 7. Treatment will not be extended beyond 18 weeks before a Visit 7 occurs. This will be recorded as a protocol deviation.

Similarly, if a participant reports a confounding adverse event within 7 days of Visit 7, Visit 7 will be rescheduled so that at least 7 days have passed since the condition was resolved. This may be outside the original +/- 3 days window for Visit 7. Treatment will not be extended beyond 18 weeks before a Visit 7 occurs. This will be recorded as a protocol deviation.

Extension Arm – Study Drug.

Some participants may not respond, or may not achieve a full response, to Tofacitinib by the end of the 16-week trial. Participants who are likely to benefit from an extension of Tofacitinib will be initially identified by the study doctor at their 8-week visit (Visit 5) using the criteria below, but may be identified as a candidate for the extension trial at subsequent visits at the study doctor's discretion if the criteria are met. Additionally,

participants must remain in good health standing and have no study doctor concerns that would preclude study continuation.

1. Alopecia areata (min. initial qualifying SALT score ≥ 25): Participant shows any decrease in their SALT score from the Baseline score, but SALT score is still ≥ 5 at the 8-week appointment.
 - In cases of alopecia totalis, observable improvement in any hair re-growth on the body would constitute a basis for Extension Arm qualification, such as eyelash or eyebrow re-growth.
 - All cases of alopecia areata present for ≥ 5 years by parent or clinician report will be invited to participate in the Extension Arm, even if no improvement decrease in SALT score is noted by 8 weeks.

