Participants will return for their 16-week visit (Visit 7) to collect the endpoints as described above. However, instead of entering a washout period after Visit 7, the participant will continue taking the IP and will return for additional visits at 28 weeks (Visit E28) and 40 weeks (Visit E40). Participants will receive an additional prescription for Tofacitinib at Visit 7 and Visit E28. Both safety labs and research labs will be collected at all Extension Arm Visits. Female participants who do not have permanent birth control will be required to take an at-home pregnancy test during the months they are not seen in clinic. Tests may be provided by the study or cost reimbursed with receipt.

The above criteria describe the minimum requirements for inclusion in the Extension Arm – Study Drug phase. Invitation to participate will continue to be subject to the study doctor's discretion and available funding for Tofacitinib.

Extension Arm – Monitoring only.

Participants may move to clinical care to receive Tofacitinib at any time, and the study team may actively facilitate this transition. If the participant begins to receive the study drug by prescription from their clinical provider, they may still remain in the Monitoring Only Extension Arm of the study. Participants will attend study visits as described above, but do not receive Tofacitinib through the clinical trial and are not subject to the inclusion criteria described above. Study participants will be asked to complete all study procedures as described, including monthly phone check-ins and medication record logs, although the Tofacitinib will no longer be managed by the Investigational Pharmacy or study team.

Washout Period.

The washout period, and collection of samples two weeks after ending the study medication (Visit 8), may be removed for all participants who continue taking Tofacitinib, either through the Extension Arm or by prescription with their personal doctor. Participants who live outside of the Denver Metro Area may opt out of returning for this study visit as well.

Additional Visits.

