At any time during the study, study doctors may request an additional study visit with a participant to address or follow-up on pressing concerns about safety or reported AEs. In this case, a study coordinator will schedule an additional study visit with the participant and their study partner as soon as possible. This visit may include collection of vitals, physical exam and recording of AEs as necessary, as well as any laboratory tests recommended by the study doctor.

Teleresearch Visits.

To facilitate participation for non-local participants, study doctors may perform a teleresearch visit using Epic. These visits may be implemented at the study doctor's discretion in place of regularly scheduled visits and combined with a remote blood draw to obtain safety labs as needed. Creatine kinase is not collected for teleresearch safety labs. Research labs may be drawn remotely and shipped to the Linda Crnic Institute. Additional study drug may be dispensed at study doctor's discretion at a prior visit in anticipation of a scheduled teleresearch visit, or shipped directly to the participant from the Investigational Pharmacy.

Remote Blood Draws.

For standard safety monitoring, it may be more convenient for the participant to have laboratory tests drawn nearer to their home. The study team may arrange for a qualified phlebotomist to visit the home and subsequent clinical analysis at an accredited lab, or for the participant to go to an alternate facility for a blood draw at their discretion. Participants may always choose to have appointments at their regular study site.

COVID-19 vaccinations and boosters.

Participants who receive a COVID-19 vaccination or booster will be advised to stop taking the study drug for 7 days (14 doses) after receiving the vaccination or booster. The original study timeline will not be altered,

unless suspension of the study drug interferes with a study endpoint (see Visit 7 Considerations for the 16-week Endpoint).

Safety and Adverse Event Monitoring.

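### Low-severity safety gap: when Visit 7 is deferred and drug continues, a participant outside the Extension Arm has no scheduled pregnancy test after week 12

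*Combined protocol and SAP*

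**What the plan says.** All references are to the combined protocol and SAP, section IV.C unless stated.

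- **Test schedule.** The "Pregnancy Test" row of Table 2 marks screening, baseline and weeks 4, 8 and 12 for everyone covered by its footnote ("For females if not surgically sterile or two years post-menopause"). Weeks 16 and 28 are marked E, Extension Arm only. The two-week post-treatment visit has no test.
- **Deferral.** Visit 7 Considerations for the 16-week Endpoint has two triggers: three or more pills missed in the preceding week, or a confounding adverse event in that week. Either makes rescheduling mandatory, possibly outside the window. Both paragraphs end with the same limit: "Treatment will not be extended beyond 18 weeks before a Visit 7 occurs". Neither mentions a pregnancy test.
- **Booster holds.** COVID-19 vaccinations and boosters sends a seven-day drug hold that interferes with an endpoint to the same rule.
- **Labs and continued drug.** Study Visits and Activities says: "Study doctors will not continue the Tofacitinib prescription without current safety labs". The same section describes the labs thus: "A blood draw will be performed for basic safety monitoring labs, which include hematology (CBC with WBC differential) and standard blood chemistry". It lists the pregnancy test as a separate screening assessment. Later visits repeat "a blood draw for the same battery of safety monitoring labs described in the screening procedures above".
- **Home tests.** Under Extension Arm – Study Drug, female participants without permanent birth control "will be required to take an at-home pregnancy test during the months they are not seen in clinic".
- **Discretionary labs.** Additional Visits allows "any laboratory tests recommended by the study doctor".
- **Status of pregnancy.** It is an exclusion criterion (section IV.B) and an individual stopping rule (Participant Discontinuation and Trial Stopping).

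**The concern.** The Table 2 pattern makes sense if a participant outside the Extension Arm takes her last dose at week 16: every stretch on drug then ends within about four weeks of a test. The deferral rule can move the last dose to week 18 without moving or adding a test. For an Extension Arm participant the week-16 test travels with Visit 7, so it is delayed rather than lost. For anyone else, Visit 7 and the post-treatment visit carry no test, so week 12 remains her last one however long dosing continues.

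At stake is patient safety. A stopping rule for pregnancy works only if pregnancy is detected, and the deferral rule extends exposure without extending the check behind that rule.

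**Working it through.** **Inputs.** Visits at weeks 0, 4, 8, 12 and 16 are days 0, 28, 56, 84 and 112, with windows of ±3 days (Study Visits and Activities). The cap is week 18, day 126 (Visit 7 Considerations). Dosing is twice daily.

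**The plan's own figures.** 16 × 7 × 2 = 224 doses, as stated under Participant Discontinuation and Trial Stopping. 15% of 224 = 33.6, rounded up to the stated 34. 15% of one week's 14 doses = 2.1, rounded up to the stated 3 pills.

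**Test spacing on drug to week 12.** 28 − 0 = 56 − 28 = 84 − 56 = 28 days.

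**Days from the week-12 test to Visit 7** (day of Visit 7 minus day of Visit 6):

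| Case | Visit 7 day | Visit 6 on day 84 | Visit 6 on day 81 |
|---|---|---|---|
| As planned | 112 | 28 | 31 |
| Latest within window | 115 | 31 | 34 |
| Adverse event resolves day 111 | 118 | 34 | 37 |
| Simple 7-day deferral | 119 | 35 | 38 |
| Adverse event resolves day 113 | 120 | 36 | 39 |
| Booster hold from day 110 | 124 | 40 (33 on drug) | 43 (36 on drug) |
| Cap (adverse event resolves day 119) | 126 | 42 | 45 |

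Adverse-event rows use the earliest permitted date, seven days after resolution. In the booster row, four pills are missed on days 110–111 (the trigger is three), the hold runs over days 110–116, compliant dosing over days 117–123, and Visit 7 falls on day 124; days on drug are elapsed days minus 7.

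**Excess over what the windows allow.**
- Cap: 45 − 34 = 11 days, equally 126 − 115.
- Simple deferral: 35 − 34 = 1 day, or 38 − 34 = 4 with an early Visit 6.
- Booster hold, days on drug: 33, inside the 34; or 36 − 34 = 2 over with an early Visit 6.

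**Doses at the cap if drug is never paused.** After week 16: (126 − 112) × 2 = 28. After the window closes: (126 − 115) × 2 = 22. Since the week-12 test: 42 × 2 = 84, against 28 × 2 = 56 planned.

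**With a test at week 16.** The longest untested stretch becomes 112 − 84 = 28 days (31 with an early Visit 6), leaving 126 − 112 = 14 days to the cap.

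**The case against.** The strongest reply is about size. The ±3-day windows already permit 34 days, so the ordinary one-week deferral barely exceeds what the sponsor accepts. With Visit 6 on schedule and Visit 7 at the earliest permitted date, the adverse-event trigger passes 34 days only if the event is still unresolved on day 112. It reaches 42 only if the event resolves around day 119 and drug is never paused. Such a participant is in contact with a study doctor, to whom every adverse event is relayed immediately and who may order tests or pause drug. Extension eligibility is broad, which shrinks the exposed group further. All of this stands, and it fixes the severity as low.

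A second reply is that Study Visits and Activities points to Table 2 for the list of safety labs, and Table 2 includes the pregnancy test. The bar on continuing the prescription might then require an up-to-date one. This stands only in part. Nothing defines when a lab is current, the text describes the safety battery as hematology and chemistry, and the Visit 7 cell excludes her. Leftover tablets could also avoid a new dispensing. The text is ambiguous at best, and a doctor's discretion is not a schedule.

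Third, the protocol never states a four-weekly rule; the 28 days is read from visit spacing, and the Extension Arm's monthly home-test rule may itself allow longer gaps. A reader might therefore infer that the deferral breaches a stated testing standard. The documents do not support that. They show only that deferral departs from the pattern Table 2 follows up to week 12.

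A reader might also take 42 days against 28, half as long again, as the typical size. That sets the worst case against the nominal plan, and the visit windows do not bear it out.

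**Conclusion.** The gap is real but minor. For a participant covered by the Table 2 footnote and outside the Extension Arm, no scheduled pregnancy test follows week 12, even when Visit 7 is deferred and drug continues. The interval from that test to Visit 7 can reach 42 days (28 planned), or 45 against the 34 that the windows allow: an excess of at most 11 days.

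This assumes that drug is not paused, that no discretionary test is ordered, and that the current-labs condition is not read as demanding a pregnancy test. The excess is material mainly when a confounding adverse event is unresolved at week 16. The number affected cannot be derived from the documents but is likely small, and they give no figure for the risk to a pregnancy.

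A reader might infer that the trial's results are touched; they are not, since no endpoint, analysis or power depends on this. Label: cheap improvement, low severity.

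**What to change.** Add one sentence to Visit 7 Considerations for the 16-week Endpoint, with a matching mark in the Table 2 pregnancy row: if Visit 7 is deferred past its window, any participant covered by the pregnancy-test footnote takes an at-home pregnancy test at about week 16, before dosing continues or resumes, and a positive result triggers the pregnancy stopping rule.

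The cost is one home test per deferred participant. The Extension Arm already uses this method and allows tests to be supplied or reimbursed. No visit, venipuncture or travel is added, and the timing of Visit 7 and its endpoints is unchanged. The wording also covers short deferrals that hardly need it, but one simple rule is easier to follow than one that depends on how long the deferral turns out to be.

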All AEs are recorded from the Baseline visit (Visit 2) when the IP begins through the final follow-up visit 2 weeks after the last Tofacitinib dose, or final visit of the Extension Arm. Additionally, AEs that occur at Screening (Visit 1) that are considered to be directly related to the screening procures will be reported. AEs are documented in terms of a medical diagnosis. When this is not possible, the AE is documented in terms of signs and/or symptoms observed by the study doctor or reported by the participant. AEs are recorded in REDCap and printed copies of the completed REDCap forms are kept in the participant’s source documentation file. AE incidence rates (number of events per 100 patient years) for the study as a whole will be calculated for monthly reports (see *Safety and Adverse Event Reporting* below).

In published studies evaluating Tofacitinib for treatment of rheumatoid arthritis, the incidence rate was as follows for various AEs: 9.4 for SAEs, 2.7 for serious infection, 3.9 for herpes zoster (shingles), 0.3 for opportunistic infection not including tuberculosis, 0.2 for tuberculosis, 0.9 for malignancies, and 0.1 for gastrointestinal perforations. These AE rates are anticipated by this study protocol and have already been deemed safe by the FDA via their approval of Tofacitinib for marketing.

When any AE, regardless of classification, is reported by a participant to any study staff, that personnel will immediately relay the AE information to a study doctor, who will classify the AE appropriately and decide if any follow-up actions should be taken. If needed, follow-up appointments will occur in a timely manner as dictated by the nature of the AE and the discretion of the PIs and study doctors. Similarly, all blood chemistry and laboratory monitoring values will be reviewed as soon as they are available by a study doctor to ensure all results are within normal ranges for a person with Down syndrome or for that specific participant. Abnormal findings will be reported as an AE as appropriate. Detailed information about every AE will be incorporated into a Monthly Progress and Safety Report, as well as Annual Reports, as described below.

Finally, any incident, experience, or outcome may be considered an unanticipated problem (UAP) if it meets the following criteria: 1) it is considered “unexpected” as defined above, 2) it is considered possibly or

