The potential risks associated with participation in the study center largely around the usage of Tofacitinib. Increased risks associated with taking Tofacitinib include: development of serious infections and sometimes fatal infections, especially in participants taking concomitant immunosuppressants; development of solid tumor cancer; laboratory abnormalities such as lymphocytosis, neutropenia, anemia, elevated liver enzymes, elevated lipids, elevated serum creatinine, and elevated blood creatine phosphokinase; nasopharyngitis; diarrhea; headache; rash; nausea; and hypertension. Additional risks may include gastrointestinal perforation. These risks will be addressed in the informed consent form.

To mitigate these risks, the design of the inclusion and exclusion criteria, as well as the study visit timeline and safety monitoring labs, have been optimized to meticulously protect participants. Individuals with any active infection and those taking concomitant immunosuppressants will be excluded from the study due to the increased risk of developing severe infections. Individuals with any history of malignant solid tumor cancers will be excluded from the study due to the increased risk of developing a malignancy. Safety monitoring will be performed at each visit to ensure participants do not develop infections or unsafe levels of cell counts, liver enzymes, lipids, creatinine, and creatine phosphokinase. Participants will see a study doctor at each of the eight visits to monitor overall health and ensure any other side effects, such as headache, nausea, diarrhea, or high blood pressure are appropriately managed and reported.

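### Participants outside Denver who stop drug at week 16 may skip their only scheduled post-dose visit, and no remote adverse-event check is required in its place

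*Combined protocol and SAP*

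**What the plan says.** Section IV.C, Safety and Adverse Event Monitoring, records all AEs from Baseline "through the final follow-up visit 2 weeks after the last Tofacitinib dose, or final visit of the Extension Arm". It makes no exception for place of residence.

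For those who stop at week 16, the follow-up visit is Visit 8. The Table 2 footnote says of it: "This visit only occurs for participants who ended Tofacitinib treatment at Visit 7." Table 2 schedules a blood count, metabolic panel, lipid panel and creatine phosphokinase there. Study Visits and Activities also gives every visit a physical exam, vital signs and AE recording. Section V (Risks, Protections from Risk, and Justifications) counts the full visit schedule among the protections: "Participants will see a study doctor at each of the eight visits to monitor overall health". Visit 8 is the eighth.

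The Washout Period paragraph then says: "Participants who live outside of the Denver Metro Area may opt out of returning for this study visit as well." It names no substitute contact.

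Three other provisions bear on the point:

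- **Teleresearch Visits.** At the study doctor's discretion, these may be held "in place of regularly scheduled visits and combined with a remote blood draw to obtain safety labs as needed". The same paragraph notes: "Creatine kinase is not collected for teleresearch safety labs." Remote Blood Draws and Additional Visits are likewise optional.
- **Phone contact.** It appears among the procedures of the Monitoring Only Extension Arm, "including monthly phone check-ins and medication record logs", but not for participants who stop at week 16.
- **Abnormal labs.** Under Participant Discontinuation and Trial Stopping, abnormal findings are to be repeated within one week.

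**The concern.** The AE window and the visit waiver do not fit together. One section promises recording for two weeks after the last dose. Another lets a group defined by residence miss the only scheduled occasion on which that recording would happen. For those participants, an empty post-dose AE record could mean that nothing happened or that nobody asked.

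The group is not hypothetical. Recruitment and Pre-Screening targets neighbouring states, invites referrals from across the country and budgets for flights.

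Section V names serious infection and laboratory abnormalities among the drug's risks. A hospitalisation shortly after stopping would probably surface through medical records. A milder infection or a silent laboratory change is much less likely to surface unless someone asks or draws blood. The first specific aim is to define the safety profile in people with Down syndrome, so uniform follow-up over the stated window is worth having.

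**Working it through.** **Reading the provisions together**

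1. AE window for a participant who stops at week 16: Baseline to week 18 (16 weeks of treatment plus 2).
2. Scheduled contacts after the last dose: Visit 8 only.
3. Visit 8 for a participant outside the Denver Metro Area: may be declined.
4. Required replacement: none found. The remote routes are permitted, not required, and none is linked to the waiver.
5. Labs: an abnormal Visit 7 value is already to be repeated within one week. What remains uncovered is a value normal at Visit 7 that becomes abnormal afterwards.

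**Inputs**

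- 47 enrolled, up to 7 lost, 16 weeks of treatment (Research Methods for Specific Aim 1; Section VII).
- Reference rates per 100 patient-years, from published rheumatoid arthritis data: 9.4 SAEs and 2.7 serious infections (Safety and Adverse Event Monitoring).
- Number of opt-outs: not given, so 10 and 20 are assumptions. The ceiling of 40 is all completers (47 − 7), with none local and none in the Extension Arm.

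**The plan's own figures reproduce**

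- Treatment time: 47 × 16/52 = 14.46 patient-years (stated as 14.5).
- Comparable SAEs: 14.46 × 9.4/100 = 1.36 (stated as 1.36).
- Stopping rate: 2/14.46 × 100 = 13.83 per 100 patient-years (stated as 13.83).

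**Time without solicited follow-up**

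Per opt-out: 2/52 = 0.038 patient-years, or 2/18 = 11% of that participant's AE window.

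For n opt-outs, time = n × 2/52 and expected events = time × rate/100:

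| Opt-outs | Patient-years | Expected SAEs | Expected serious infections |
|---|---|---|---|
| 10 | 0.38 | 0.04 | 0.01 |
| 20 | 0.77 | 0.07 | 0.02 |
| 40 (ceiling) | 1.54 | 0.14 | 0.04 |

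These figures assume that on-drug rates persist for two weeks after the last dose and that nothing is captured passively. Both assumptions tend to raise the figures. In the other direction, the protocol expects that people with Down syndrome may be more prone to AEs than the reference population. Doubling the SAE rate would give 2 × 0.036 = 0.07 expected SAEs for 10 opt-outs.

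**The case against.** **The remote routes were written for these people.** The waiver covers returning, that is, the trip. The Teleresearch section follows shortly after, is aimed at non-local participants and can replace any scheduled visit. This is the best reply and it narrows the point. But the text does not say that a remote contact happens when Visit 8 is declined. If that is the intent, one sentence would state it. Figure 6, the visit timeline, was not legible in the copy used. A remote contact shown there would settle the matter.

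**AEs can still come in unasked.** When an AE "is reported by a participant to any study staff, that personnel will immediately relay the AE information to a study doctor". Medical records are also accessed during the trial. Both routes stand, and they make a missed hospitalisation unlikely. Neither asks about symptoms or draws blood.

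**Visit 7 is a full safety visit, and abnormal labs are repeated.** This also stands. The repeat rule sits among the individual stopping rules, but its wording has no residence exception. It limits the lab gap to values that change after Visit 7. It also makes a separate creatine kinase instruction unnecessary, even though teleresearch labs omit that test.

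**Sparing travel after the last endpoint visit is reasonable.** Agreed. A participant must bring a guardian or study partner to every visit, and no efficacy endpoint uses Visit 8. The waiver itself should stay.

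**A reader might infer that the AE rates per 100 patient-years would be understated.** The documents do not support that as a general claim, because the denominator is not defined. The only person-time they compute is treatment time. Suppose the event rate is constant and post-dose events are divided by treatment time alone. Full Visit 8 capture would then overstate the rate: (14.46 + 1.54)/14.46 = 16.00/14.46 = 1.106. On that denominator, opt-outs would move the estimate towards the true rate. The direction of any error depends on a choice the plan leaves open.

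**Conclusion.** The point holds as a gap between the stated AE window and the visit waiver. Non-local participants who stop at week 16 can leave the study with no solicited AE check and no safety labs after the last dose, and the plan would still have been followed exactly.

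The size is small: 0.038 patient-years per opt-out and about 0.04 expected SAEs per 10 opt-outs, on the assumptions given. The true number of opt-outs is unknown.

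A reader might also infer that the primary safety endpoint is compromised. It is not. Outcome Measures and Section VII define it over the 16-week period, which closes before Visit 8. The loss falls on post-treatment AE and laboratory follow-up.

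This is a cheap improvement, and nothing in the trial's main conclusions turns on it. Confidence is moderate, because sites may already use the remote routes in practice.

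**What to change.** Add to the Washout Period paragraph: when the in-person Visit 8 is waived for a participant who has stopped tofacitinib, study staff will collect AEs and SAEs 2 weeks after the last dose by phone or teleresearch visit, and will offer the Visit 8 safety labs as a remote draw.

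If the AE rates per 100 patient-years are to include post-dose events, state that the denominator includes post-dose person-time and counts only the time actually observed.

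The cost is one short remote contact per opt-out, and possibly a local blood draw, through routes the protocol already has. The travel waiver is kept. Because the draw is offered and not compulsory, a participant who declines it would still have no post-dose labs, but would have been asked about AEs.
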